Efficacy measurements		•									
sUA, creatinine, eGFR, Cystatin C, NT-proBNP		х	x	х	х	x	х	х	х	х	Section 8.1
UACR - First morning void samples from 3 days before visit		x	x	х	x	x	х	x	х	x	Section 8.1
CCI											
CCI											
CCI											
Optional genetics sampling	•	•									
Blood sample			X								Section 8.7
Study treatment dispensing ⁱ											
Randomisation			х								Section 6.3
Titration step 1 dose dispensed			Х								Section 6.1
Titration step 2 dose dispensed				х							Section 6.1
Final (Titration step 3) dose dispensed					Xj	Xj	Xj	Xj	Xj	X ^{j,b}	Section 6.1

Table 1 Schedule of activities (SoA), screening and treatment period

CONFIDENTIAL AND PROPRIETARY

Visit	1 (Pre- Screening)	2 (Screening)	3 (Randomis ation)	4	5	6	7	8 (Primary Analysis)	9 ^a	10 ^a See EOT visit in Table 2	Details in CSP section or Appendix
Week	-6 to -1	-4 to 0	0	4	8	12	20	34	47	60	
Window			NA	±7d	±7d	±7d	±7d	±7d	±7d	±7d	
Study treatment returned				х	Х	x	х	x	х	х	Section 6.2

Table 1 Schedule of activities (SoA), screening and treatment period

CSP Clinical study protocol; eGFR Estimated glomerular filtration rate; EOT End of treatment; FMV First morning void; FU follow up; IP Investigational product; CCI NA Not applicable; NT-proBNP N-terminal pro-brain natriuretic peptide; PK Pharmacokinetic; PWV Pulse wave velocity; sUA Serum uric acid; UACR urinary albumin to creatinine ratio

At the time of implementation of Protocol Version 5.0 (refer to Section 4.1.1 for description of implementation), a new dosing regimen will be introduced to assess the higher dose of 24 mg verinurad. Patients in the 3 mg verinurad cohort who will have Visit 9 planned after the amendment is implemented in the respective country will be switched to 24 mg dose at Visit 9. Patients will only be allowed to switch to the new dosing regimen's treatments introduced under Protocol Version 5.0 if the patient's eGFR was \geq 30 mL/min/1.73m² at Visit 8. Management of patients with eGFR <30 mL/min/1.73m² at Visit 9 should be discussed with the medical monitor.

Patients who do not tolerate the new dosing regimen will be down-titrated to the initial dosing regimen (ie, patients on 24 mg will be down-titrated to 3 mg, and patients in other cohorts will not be dispensed the matching placebo capsule).

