A patient in the new dosing regimen who is still on treatment, who has not been down-titrated and has signed Informed Consent Form for the new dosing regimen, will receive the new treatment at Visit 9. Patients who do not consent should be discontinued from the study at a subsequent visit. If the patient has passed Visit 9 before the dates listed above, they will remain on the initial dosing regimen.

Additional details on treatment administration are included in Section 6.1.

Target patient population

The study will be conducted in male and female adults (\geq 18 years of age) with documented CKD who provide informed consent to participate in the study and are not pregnant. Eligible patients will have sUA concentrations \geq 6.0 mg/dL, eGFR \geq 25 mL/min/1.73 m² and a UACR between 30 mg/g and 5000 mg/g (inclusive). Patients should be receiving stable treatment of angiotensin converting enzyme inhibitor (ACEi) or angiotensin receptor blocker (ARB) for at least 1 month prior to entry into the study.

Patients with a prior history of gout will receive gout prophylaxis treatment with colchicine up to 0.6 mg once daily, as outlined in gout guidelines. If intolerance or other sound medical rationale exists for not using colchicine, the investigator may instead prescribe gout flare prophylaxis with steroids or non-steroidal anti-inflammatory drugs (NSAIDs), or avoid administering prophylaxis altogether. Prophylaxis against flares will be fully explained and discussed with the patient.

Study period

Estimated date of first patient enrolled: Q3 2019

Estimated date of last patient completed: Q4 2021

Number of patients

Total of 725 patients (145 per arm [initial dosing regimen]) at around 200 sites in approximately 15 countries will be randomised with equal probability to 1 of 5 treatment arms.

Treatments and treatment duration

Each patient will be treated as randomised with placebo, allopurinol, and/or verinurad plus allopurinol (3 doses) for 26 weeks at target dose after 8 weeks of titration to allow for assessment of the primary endpoint, UACR at 6 months. After Protocol Version 5.0 is implemented, patients will continue treatment at target dose for approximately 12 weeks after Visit 9, and will discontinue therapy at Visit 10. Patients who have already had IP administered at Visit 9 or a subsequent visit before Protocol Version 5.0 is implemented will discontinue IP at the next subsequent visit.

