4.1.2.9 Week 47 (Visit 9)

At the time of implementation of Protocol Version 5.0, a new dosing regimen will be introduced to assess the higher dose of 24 mg verinurad. Patients in the 3 mg verinurad cohort

who will have Visit 9 planned after the amendment implementation in the respective country/site and who have signed ICF for the new dosing regimen will be switched to 24 mg dose at Visit 9. Patients who do not consent should be discontinued from the study at a subsequent visit.

To introduce the new 24 mg dose, a new dosing regimen will be initiated across treatment arms to maintain blinding. For verinurad dosing, all patients in the new dosing regimen will receive 2 capsules through addition of a matching placebo capsule, with the exception of those who switched from the 3 mg to 24 mg dose, where two 12-mg verinurad capsules will be given. Allopurinol dosing will remain the same.

Note: Patients will only be allowed to switch to the new dosing regimen's treatments introduced under Protocol Version 5.0 if the patient's eGFR was \geq 30 mL/min/1.73m² at Visit 8. Management of patients with eGFR <30 mL/min/1.73m² at Visit 9 should be discussed with the medical monitor.

- Place phone calls on the day before the visit to remind patients to record the time and date of the study medication intake on the day of the visit
- Collect first morning void samples from 3 days before visit
- Collect untaken study medication
- Update concomitant medication
- Record AEs
- Record vital signs
- Record weight
- Obtain blood samples for post-dose PK and sUA (drug taken at home, date and time of drug intake should be recorded)
- Obtain blood samples for efficacy assessments (s-UA, creatinine, eGFR, Cystatin C, NTproBNP)
- Perform pregnancy urine dipstick test for women of childbearing potential; after 2 positive urine tests, a serum pregnancy test is to be done by central laboratory
- Prior to Protocol Version 5.0, IVRS/IWRS and dispense titration Step-3 dose (Note: Titration to step-3 target dose will only be allowed if the patient's eGFR was ≥30 mL/min/1.73m² at Visits 3 and 4.)
- Dispense containers for morning voids

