6.3 Measures to minimise bias: randomisation and blinding

All patients will be centrally assigned to randomised study treatment using an IVRS/IWRS. Before the study is initiated, the telephone number and call-in directions for the IVRS and/or the log-in information and directions for the IWRS will be provided to each site.

Patients who meet the eligibility criteria will be randomised in a 1:1:1:1:1 ratio to high, intermediate or low dose of verinurad plus allopurinol, allopurinol or placebo.

Laboratory reports for sUA and UACR will be masked to guard against revealing group differences in treatment endpoints except during pre-screening and screening. The central laboratory will issue notifications to study sites if sUA or UACR values indicate potential health concerns.

If a patient withdraws from the study, then his/her enrolment/randomisation code cannot be reused. Withdrawn patients will not be replaced.

The IVRS/IWRS will provide to the investigator(s) or pharmacists the kit identification number to be allocated to the patient at the dispensing visit. Routines for this will be described in the IVRS/IWRS user manual that will be provided to each centre. For patients who need down titration, the investigator will need to use the IVRS/IWRS for allocation of new study drug kits for the lower dose.

The randomisation code should not be broken except in medical emergencies when the appropriate management of the patient requires knowledge of the treatment randomisation. The investigator documents and reports the action to AstraZeneca, without revealing the treatment given to patient to the AstraZeneca staff.

AstraZeneca retains the right to break the code for SAEs that are unexpected and are suspected to be causally related to an IP and that potentially require expedited reporting to regulatory authorities. Randomisation codes will not be broken for the planned analyses of data until all decisions on the evaluability of the data from each individual patient have been made and documented.

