After initiation of study medication, if a patient experiences signs or symptoms suggestive of nephrolithiasis (eg, flank pain or haematuria), he/she should be evaluated by a physician, and serum creatinine, blood urea nitrogen, and urinalysis should be measured via central laboratory testing (preferred) and/or local laboratory testing, as appropriate, to determine renal function. Imaging (intravenous urogram, renal ultrasound, or MRI) is recommended to confirm or exclude any urinary tract calculus. Abnormal results should be treated as medically appropriate by the treating physician. All symptoms, testing, and results will be documented in source documents and the CRF.

If a patient develops a urinary tract calculus (as confirmed and documented by imaging or passage of a stone) at any time during the study, the patient will discontinue randomised study medication and be encouraged to remain in the study for continued safety assessments. If the urinary tract calculus is passed, it should be collected and submitted to pathology for analysis of chemical composition.

F 2 Deterioration of renal function

This study will have at least 2 pre-dose serum creatinine measurements. The (higher) of all creatinine measurements collected before randomisation will be considered the baseline serum creatinine for renal safety monitoring.

This study enrols patients with chronic kidney disease (CKD). These patients may have changes in serum creatinine and estimated glomerular filtration rate (eGFR) that may be due to various causes such as: deterioration of renal function due to the underlying cause of CKD, volume depletion, hypotension, intercurrent medical conditions such as worsening heart failure, concomitant drugs that alter renal tubular creatinine secretion or reabsorption, or change in glomerular filtration rate via haemodynamic effects.

The investigator should assess each patient carefully to determine the most likely cause for the deterioration of renal function. Following a thorough assessment, the patient should be managed according to local medical practice. Potentially-treatable causes such as volume depletion, hypotension etc, should be corrected before following the recommendations given below.

Patients on ACEi/ARB medication (CKD, heart failure) or on mineralocorticoid receptor antagonists or beta-blockers (heart failure) should not have these treatments reduced in dose or discontinued unless all other measures fail to improve the patient's situation.

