F 2.1 Patients with baseline eGFR \geq 40 mL/min/1.73 m²

F 2.1.1 Serum creatinine increase to \geq 1.5-fold from baseline

- Assess the patient to identify and manage any potential contributing factor. Correct any dehydration and ensure the patient is well hydrated prior to next renal safety monitoring visit.
- At the investigator's discretion, the patient may continue with study treatment, and retest of serum creatinine should be performed the following week. If the underlying cause (eg, dehydration) is still present at the next evaluation, the investigator should carefully consider if the retesting should be postponed for another week.
- Patient should attend the following week for repeat serum creatinine measurement. If an underlying potentially treatable cause (eg, dehydration) is still present, the investigator should treat this appropriately and postpone testing for up to a week.
- Subsequent management will depend on the repeat measurement(s):
 - If serum creatinine <1.5-fold of baseline value for two successive measurements, the patient may restart/continue with study treatment and the original study visit schedule.
 - If repeat serum creatinine is between ≥1.5 to <2.0-fold of baseline value, the patient should be evaluated every 1 to 2 weeks. During this evaluation period, the randomised treatment can be temporarily interrupted at the investigator's discretion. If serum creatinine is <1.5-fold of baseline value during the evaluation period, study treatment may be restarted/continued on the original study visit schedule.
 - If serum creatinine ≥2.0-fold of baseline value for 2 successive measurements (including the original high value if applicable), randomised treatment should be permanently discontinued and the patient should be followed up as per study schedule.

F 2.2 Patients with baseline eGFR <40 mL/min/1.73 m²

The CKD-EPI formula (Michels et al 2010) should be used to estimate GFR for enrolment criteria, baseline value and subsequent on-study measurements.

More intense renal monitoring and discontinuation are based on % drop from the baseline value.

F 2.2.1 If eGFR drops to <75% of the baseline value

- Assess the patient to identify and manage any potential contributing factor. Correct any dehydration and ensure the patient is well hydrated prior any future evaluation.

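### The Visit 9 switch to 24 mg has only absolute eGFR limits and does not refer to Appendix F, so a 3 mg patient kept on drug with an unresolved 1.5- to under 2-fold creatinine rise can still qualify if eGFR stays at 30 or more

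*Supplement*

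**What the plan says.** **Switch rule.** From Protocol Version 5.0, eligible patients randomised to 3 mg verinurad move to 24 mg at Visit 9 (Week 47). There are two renal provisions, both at an absolute eGFR of 30 mL/min/1.73 m² (Table 1 footnote a, 4.1.2.9, 6.1.1):

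- Visit 8: "Patients will only be allowed to switch to the new dosing regimen's treatments introduced under Protocol Version 5.0 if the patient's eGFR was" at least 30.
- Visit 9: management of an eGFR below 30 "at Visit 9 should be discussed with the medical monitor".

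The other conditions, apart from the calendar dates, are in sections 1.2 and 4.1.1: "A patient in the new dosing regimen who is still on treatment, who has not been down-titrated and has signed Informed Consent Form" receives the new treatment. Section 6.6 repeats that down-titrated patients do not switch.

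**Renal monitoring.** Appendix F 2 sets the reference value: the higher "of all creatinine measurements collected before randomisation will be considered the baseline serum creatinine for renal safety monitoring". For baseline eGFR of 40 or more, Appendix F 2.1.1 starts at a 1.5-fold creatinine rise: "At the investigator's discretion, the patient may continue with study treatment, and retest of serum creatinine should be performed the following week". If the repeat is still 1.5- to under 2-fold, the patient is reviewed every 1 to 2 weeks. "During this evaluation period, the randomised treatment can be temporarily interrupted at the investigator's discretion". Once creatinine is below 1.5-fold, "study treatment may be restarted/continued on the original study visit schedule". Permanent discontinuation needs two successive values of 2-fold or more.

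**The concern.** The two sets of rules measure different things. The switch looks at absolute eGFR, while Appendix F 2.1.1 looks at change from the patient's own baseline. A patient with a fairly high baseline can have a rise that Appendix F treats as needing frequent review and still be above 30.

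The condition of not having been down-titrated does not catch this patient. Section 8.4.5 sends mild intolerance to down-titration but creatinine elevations to Appendix F, which has no down-titration step. Section 7.1.1, under which the last dose taken is given again, applies only after an interruption.

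Section 2.3 names creatinine elevation as the main toxicity of concern with verinurad monotherapy. Read literally, the switch rule raises verinurad eight-fold, without titration, while that marker is elevated and the evaluation is still open.

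**Working it through.** No planned figure is in dispute. The check is whether a patient can satisfy both sets of rules, and how many might.

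**1. Lowest baseline eGFR that escapes both limits.** The protocol cites the CKD-EPI formula without printing it. Assumption: eGFR varies as creatinine to the power −k, with k from 1.0 to 1.2. After an r-fold creatinine rise, eGFR is 30 or more if baseline ≥ 30 × r^k.

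| Creatinine ratio r | k = 1.0 | k = 1.2 |
|---|---|---|
| 1.5 | 45.0 | 48.8 |
| 1.75 | 52.5 | 58.7 |
| 1.99 | 59.7 | 68.5 |

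The lower pair applies only at 1.5-fold. A baseline of 50 falls below 30 once r exceeds (50/30)^(1/k), that is 1.53 (k = 1.2) to 1.67 (k = 1.0). To stay above 30 across the whole band, the baseline must be about 60–69. Such baselines are plausible here: entry has no upper eGFR limit, and the Phase 2a arm means were 59 and 68 (section 1.2).

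**2. Lower Appendix F tier.** For baseline below 40, monitoring starts below 75% of baseline. At 39.9 this is 0.75 × 39.9 = 29.9, already under 30. The absolute limits cover this tier.

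**3. How long the evaluation would have to stay open.** Scheduled creatinine is taken at Weeks 34 and 47, with none between. An evaluation open since Visit 8 would have run 47 − 34 = 13 weeks, or 13/2 = 6.5 to 13/1 = 13 re-checks, without resolving, being interrupted or reaching 2-fold twice. Otherwise it must have begun with an unscheduled sample. In that case the Visit 8 bar was already passed, and only the Visit 9 medical-monitor provision remains.

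**4. Expected numbers.** The documents give no prevalence, so both inputs are assumptions. About half of the planned patients are expected on the new regimen, and 145/2 is about 72 in the low-dose arm; 50 allows for losses. Let p be the fraction in an open evaluation on drug at Visit 9.

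| p | Low-dose patients (n = 50 to 72) | All five arms (5 × n × p) |
|---|---|---|
| 0% | 0 | 0 |
| 0.5% | 0.25–0.36 | 1.25–1.8 |
| 1% | 0.50–0.72 | 2.5–3.6 |
| 2% | 1.00–1.44 | 5.0–7.2 |

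These counts do not remove patients whose eGFR has fallen below 30, so they lean high.

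**5. Precision cost of a hold.** If a fraction p of each arm does not switch, the standard error of the 12-month comparison of 24 mg with placebo (9.4.2.2) grows by (1 − p)^−0.5. At 2% this is 0.98^−0.5 = 1.010, about 1%.

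**The case against.** The case against is substantial.

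- **Safeguards exist.** Section 8.4.5 requires creatinine elevations to be managed under Appendix F. Section 8 sends immediate safety concerns to the sponsor. Section 8.3.9 makes clinically significant acute creatinine changes events of special interest, and the data monitoring committee sees unblinded data (8.4.6). All of this stands, but none of it mentions the dose step or stops it.
- **Appendix F may imply a hold.** Treatment proceeds on the original visit schedule once creatinine is below 1.5-fold, and the switch is part of that schedule. This is a fair reading. However, the text does not mention the switch, and the Visit 9 section does not point back to it.
- **The risk evidence is reassuring.** Three combination studies reported no creatinine elevations. The Phase 2a CKD study, in a similar population, had equal rates on active treatment and placebo, although at 9 mg with febuxostat (2.3). Interim Cmax was less than half of that expected. Cmax at 24 mg is expected to be below that seen in healthy subjects over 7 days without safety concerns (4.3). This stands and lowers the priority.

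A reader might infer that the escalation would go unnoticed. The documents do not support that: section 6.3 says "Laboratory reports for sUA and UACR will be masked to guard against revealing group differences in treatment endpoints", and creatinine is not on that list. The investigator can see the rise, knows that a switch may mean 24 mg, and may interrupt drug in any arm. Nor does every patient with a baseline above 45–49 qualify throughout the 1.5- to under 2-fold band; step 1 shows that many fall below 30.

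**Conclusion.** The gap is real but small. A 3 mg patient with baseline eGFR of 40 or more, kept on drug in an open Appendix F 2.1.1 evaluation with eGFR still at 30 or more, meets every written condition for going to 24 mg. Whether the step is withheld then depends on individual judgement, chiefly the investigator's decision to interrupt, and not on the switch rule.

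The baseline thresholds rest on the assumed exponent of 1.0 to 1.2. The expected count of about zero to one low-dose patient rests on assumed prevalences of 0–2% and 50–72 low-dose switchers. The documents do not show that 24 mg would harm such a patient, and the combination data point towards few cases. This is a cheap improvement to a low-frequency safety rule. It does not challenge the dose extension or the primary analysis at Week 34, which precedes the switch.

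**What to change.** Add one sentence, for all arms, wherever the switch conditions are stated (Table 1 footnote a, 1.2, 4.1.1, 4.1.2.9, 6.1.1):

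*Patients under an unresolved Appendix F 2.1.1 evaluation when drug is dispensed at Visit 9 (most recent creatinine at least 1.5 times the Appendix F baseline) will not switch and will continue their current treatment.*

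This uses the route that section 6.1.1 already has for down-titrated patients, and applying it to every arm keeps the blind. No clause is needed for baseline eGFR below 40, which the limits at 30 already cover. A rise first seen in the Visit 9 sample can be left to the existing Appendix F retest and interruption rules and the existing return to the initial regimen.

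**Cost.** One sentence in five places and one check at Visit 9 dispensing, with no new visit or sample. On the assumed prevalences, about 0–1.4 patients per arm would not switch, which widens the standard error of the 12-month comparison by about 1% at 2%. The switched groups also become slightly more selected on creatinine. This should be noted when the 12-month creatinine and eGFR comparisons are interpreted, since both are secondary endpoints.

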1.2 Synopsis

Protocol title

A Phase 2b, Multicentre, Randomised, Double-blind, Placebo-controlled Study of VerinurAd and AlloPurinol in Patients with CHronic KIdney Disease and HyperuRicaEmia

Short Title: SAPPHIRE

Rationale

Evidence shows independent associations between hyperuricaemia (elevated serum uric acid [sUA]) and the risk of hypertension, myocardial infarction, chronic kidney disease (CKD), type 2 diabetes, heart failure, and metabolic syndrome, including obesity (Nakagawa et al 2006, Grayson et al 2011, Kodama et al 2009, Leyva et al 1998, Anker et al 2003). Furthermore, gout, an inflammatory arthritis caused by deposition of monosodium urate crystals in joints, is associated with an increased risk of all-cause death, as well as cardiovascular (CV) death (Iochimescu et al 2008, Kim et al 2008, Niizeki et al 2006, Jankowska et al 2007). Hyperuricaemia is a prerequisite for development of gout, thus linking high levels of sUA to gout and to poor outcomes. However, the causal relationship between hyperuricaemia and/or gout and the aforementioned diseases and outcomes remains to be proven.

Uric acid transporter 1 (URAT1) is responsible for reabsorption of uric acid (UA in the proximal tubule. Inhibition of URAT1 results in increased urinary excretion of UA. Verinurad (RDEA3170) is a novel URAT1 inhibitor in Phase 2 development for chronic kidney disease and heart failure. Verinurad combined with the xanthine oxidase (XO) inhibitors (XOI) febuxostat or allopurinol has been shown to lower sUA in patients with recurrent gout in Phase 2 studies by up to 80% (see Investigator's Brochure, Section 5.2.1.3-4 for details on Studies 204, 205, and 206). The extensive lowering of sUA delivered presents a unique opportunity to explore whether intensive urate lowering therapy can improve kidney function and/or cardiac health.

Potent URAT1 inhibition has been associated with creatinine elevation in some patients, potentially related to increased peak concentrations of urinary uric acid (uUA) in the proximal tubuli of the kidney. Verinurad is therefore given as an extended release formulation as a low maximum concentration is expected to further reduce or eliminate the risk of creatinine elevations. Moreover, verinurad is to be developed exclusively in a fixed-dose combination with an XOI, reducing also the production of UA.

The Phase 2a study D5495C00007 was performed using 9 mg verinurad given as the ER8 capsule and 80 mg febuxostat administered once daily in combination for 24 weeks. The primary endpoint was change in urinary albumin to creatinine ratio (UACR) at 12 weeks.

Sixty patients were randomised. At enrolment, the treatment arms in study D5495C00007 were generally balanced with regards to common clinical parameters.

The study met the primary endpoint at 12 weeks. UACR was significantly reduced by 39.4% for patients randomised to be treated with verinurad and febuxostat compared to placebo (p=0.0747). The comparison between the active arm and the control arm indicated statistical significance was achieved, considering the predetermined alpha (0.1). The effect on UACR was rapid, with full effect achieved at the first on-treatment assessment time point at 1 week, and did not appear to be driven by outliers.

Mean baseline estimated glomerular filtration rate (eGFR) in the trial was 59 and 68 mL/min/ 1.73 m^2 in the active and control arms, respectively. There were no changes in eGFR in either arm, either at the early or late assessment time points. However, considering the limited sample size, eGFR variability, and short duration of treatment, this is not unexpected.

For full data, including safety results, see the Investigator's Brochure.

Objectives	Endpoint/variable:
Primary objective:	
To assess the effects of treatment with verinurad and allopurinol, allopurinol alone, and placebo on UACR at 6 months	Change from baseline in UACR at 6 months
Secondary objectives:	
To assess the effects of treatment with verinurad and allopurinol, allopurinol alone, and placebo on UACR at 12 months	Change from baseline in UACR at 12 months
To assess the effects of verinurad and allopurinol, allopurinol alone, and placebo on sUA	Change from baseline in sUA at 6 and 12 months
To estimate the dose-response relationship among 3 doses of verinurad and allopurinol and placebo on UACR and sUA	Change from baseline in UACR and sUA at 6 months
To assess the effects of verinurad and allopurinol versus placebo on kidney function	Change from baseline in estimated glomerular filtration rate at 6 and 12 months Change from baseline in creatinine at 6 and 12 months Change from baseline in cystatin-C at 6 and 12 months
CCI	

Objectives and endpoints

Objectives	Endpoint/variable:

Objectives	Endpoint/variable:
CCI	
	I
Safety objective:	Endpoint/variable:
To assess the safety and tolerability of intensive UA	Rates of AEs and SAEs, including CV events
lowering therapy with verinurad and allopurinol	Changes in vital signs, electrocardiograms, and clinical laboratory parameters

AE Adverse event; ALT alanine transaminase; AST aspartate transaminase; CV cardiovascular; eGFR estimated glomerular filtration rate; NT-proBNP N-terminal pro-brain natriuretic peptide; PD pharmacodynamic; SAE serious adverse event; sUA serum uric acid; UA uric acid UACR urinary albumin to creatinine ratio Months 6 and 12 are specified as elapsed time after the 8-week titration period. Thus, Month 6 is at 34 weeks of treatment and Month 12 is at 60 weeks of treatment.

Overall design

This is a randomised, double-blind, placebo-controlled, parallel, global, dose-finding, Phase 2b study to assess the efficacy and safety of verinurad and allopurinol in patients with CKD and hyperuricaemia. Patients who meet the eligibility criteria will be randomised in a 1:1:1:1:1 ratio to high, intermediate or low dose of verinurad plus allopurinol, allopurinol or placebo. As of Protocol Version 5.0 and following a blinded interim analysis in September 2020, the study design was modified to include a new dosing regimen. All patients with Visit 9 (47 weeks) occurring after implementation of the amendment and investigational product (IP) is available (approximately 01 May 2021, ie, approximately half of planned patients randomized) will be treated with the new dosing regimen. Under the new dosing regimen all patients will continue with the same dose of verinurad and allopurinol as previously, except patients randomized to the low dose of verinurad (3 mg), which will be switched to treatment with 24 mg verinurad. Also, following implementation of the amendment, all subjects will discontinue therapy after 60 weeks (Visit 10). Patients that have conducted Visit 10 before the implementation of the amendment will discontinue therapy at their next scheduled visit.

The new treatment regimen will be dispensed to patients for which Visit 9 falls on or after the last of the following dates:

- the date of availability at site of IP suitable for the new treatment regimen,
- the date of the Regulatory Authority approval of Protocol Version 5.0 in the respective country, and
- the date of the Ethics Committee/Independent Review Board approval of Protocol Version 5.0 in the respective country/site.

A patient in the new dosing regimen who is still on treatment, who has not been down-titrated and has signed Informed Consent Form for the new dosing regimen, will receive the new treatment at Visit 9. Patients who do not consent should be discontinued from the study at a subsequent visit. If the patient has passed Visit 9 before the dates listed above, they will remain on the initial dosing regimen.

Additional details on treatment administration are included in Section 6.1.

Target patient population

The study will be conducted in male and female adults (\geq 18 years of age) with documented CKD who provide informed consent to participate in the study and are not pregnant. Eligible patients will have sUA concentrations \geq 6.0 mg/dL, eGFR \geq 25 mL/min/1.73 m² and a UACR between 30 mg/g and 5000 mg/g (inclusive). Patients should be receiving stable treatment of angiotensin converting enzyme inhibitor (ACEi) or angiotensin receptor blocker (ARB) for at least 1 month prior to entry into the study.

Patients with a prior history of gout will receive gout prophylaxis treatment with colchicine up to 0.6 mg once daily, as outlined in gout guidelines. If intolerance or other sound medical rationale exists for not using colchicine, the investigator may instead prescribe gout flare prophylaxis with steroids or non-steroidal anti-inflammatory drugs (NSAIDs), or avoid administering prophylaxis altogether. Prophylaxis against flares will be fully explained and discussed with the patient.

Study period

Estimated date of first patient enrolled: Q3 2019

Estimated date of last patient completed: Q4 2021

Number of patients

Total of 725 patients (145 per arm [initial dosing regimen]) at around 200 sites in approximately 15 countries will be randomised with equal probability to 1 of 5 treatment arms.

Treatments and treatment duration

Each patient will be treated as randomised with placebo, allopurinol, and/or verinurad plus allopurinol (3 doses) for 26 weeks at target dose after 8 weeks of titration to allow for assessment of the primary endpoint, UACR at 6 months. After Protocol Version 5.0 is implemented, patients will continue treatment at target dose for approximately 12 weeks after Visit 9, and will discontinue therapy at Visit 10. Patients who have already had IP administered at Visit 9 or a subsequent visit before Protocol Version 5.0 is implemented will discontinue IP at the next subsequent visit.

Study treatments will be titrated in discrete steps as shown in Table 3. Titration steps will be spaced at 4-week intervals to minimise the risk of skin reactions to allopurinol. Patients unable to tolerate the stepped dosage may be down-titrated only by reversing the assigned steps within treatment group, and verinurad and allopurinol dosages cannot be unpaired from the titration schedule. Patients who cannot tolerate the step-1 titration will be discontinued from IP and be followed for the remainder of the study.

	Step 1 - titration	Step 2 - titration	Step 3 - target dose
	(verinurad/ allopurinol)	(verinurad/ allopurinol)	(verinurad/ allopurinol)
High Dose (mg)	3/100	7.5/200	12/300
Intermediate Dose (mg)	3/100	7.5/200	7.5/300
Low Dose (mg)	3/100	3/200	3/300
Allopurinol alone (mg)	0/100	0/200	0/300
Placebo (mg)	0/0	0/0	0/0

Table 3Titration schedule

At the time of implementation of Protocol Version 5.0, a new dosing regimen will be introduced to assess a higher dose of 24 mg verinurad. Patients in the 3 mg verinurad cohort who will have Visit 9 planned after the amendment implementation in the country/site and who have signed ICF for the new dosing regimen will be switched to 24 mg dose at Visit 9.

Patients who do not consent should be discontinued from the study at a subsequent visit. To introduce the new 24 mg dose, a new dosing regimen will be initiated across treatment arms to maintain blinding. For verinural dosing, all patients in the new dosing regimen will receive 2 capsules through addition of a matching placebo capsule, with the exception of those who switched from the 3 mg to 24 mg dose, where two 12-mg verinurad capsules will be given. Allopurinol dosing will remain the same.

When the new dosing regimen is introduced under Protocol Version 5.0, patients who were down-titrated due to intolerance in the initial dosing regimen will not switch treatment to the new dosing regimen. These patients will instead remain on the same treatment after Visit 9.

Patients who do not tolerate the new dosing regimen will be down-titrated to the initial dosing regimen (ie, patients on 24 mg will be down-titrated to 3 mg, and patients in other cohorts will not be dispensed the matching placebo capsule). If there is a need for further down-titration, patients will follow the down-titration steps outlined in the initial dosing regimen (Section 6.1). Additionally, patients in the initial dosing regimen will follow down-titration steps outlined for the initial dosing regimen (Section 6.1).

Data monitoring committee

An independent data monitoring committee (DMC) will be appointed and will report to AstraZeneca and the contract research organisation (CRO). The DMC will be responsible for ensuring patient safety by assessing the safety of the IP during the study, and for reviewing the overall conduct of the study. The DMC will have access to the individual treatment codes and be able to merge these with the collected study data while the study is ongoing.

Clinical event adjudication committee

The role of the clinical event adjudication committee (CEA) is to independently review, interpret and adjudicate potential CV events that are experienced by the patients. CV events will be identified preliminarily by the investigators, and also by AstraZeneca personnel, CRO personnel or in the CEA process as specified in the CEA charter. The CEA member/s will not have access to individual treatment codes for any patient or clinical efficacy endpoint and safety event.

Statistical methods

The estimated sample size of 145 patients per arm (initial dosing regimen) will yield 80% power to detect a 25% reduction in UACR for the high dose of verinurad + allopurinol compared to placebo (treatment difference of approximately -0.29 on natural log scale) at the two-sided alpha level of 0.1, assuming a standard deviation of 1.0 on the natural log-scale. A total of 725 patients (145 patients per arm [initial dosing regimen]) need to be randomised.

The primary efficacy variable is the change from baseline in UACR at 6 months. The analysis of change in UACR from baseline to Week 34 (including the 8-week titration phase) will be conducted on the log-transformed UACR values using repeated measures model. This analysis will be performed on the Full Analysis Set (FAS).

Three hypotheses will be included in confirmatory testing for the primary objective. The following hypotheses will be tested sequentially at two-sided alpha = 0.1:

- Null hypothesis: No difference between high dose verinurad plus allopurinol compared to placebo on UACR at 6 months
- Alternative hypothesis: There is a difference between high dose verinurad plus allopurinol compared to placebo on UACR at 6 months
- Null hypothesis: No difference between high and intermediate dose verinurad combined plus allopurinol compared to allopurinol alone on UACR at 6 months
- Alternative hypothesis: There is a difference between high and intermediate dose verinurad combined plus allopurinol compared to allopurinol alone on UACR at 6 months
- Null hypothesis: No difference between allopurinol alone compared to placebo on UACR at 6 months
- Alternative hypothesis: There is a difference between allopurinol alone compared to placebo on UACR at 6 months

No other comparisons between treatment groups for the primary and secondary objectives will be adjusted for multiplicity.

